9.3 VARIABLES

9.3.1 Variables for All Participants with PNH

9.3.1.1 Crovalimab Exposure

The Crovalimab Silo is an observational study. No study medication will be provided as part of participation. Dosing and treatment duration of crovalimab are at the discretion of the physician in accordance with local clinical practice and local labeling.

Crovalimab exposure will be defined as the duration from the date of silo enrollment until crovalimab discontinuation date, plus 12 months if the participant with PNH does not start a new complement inhibitor or plus 12 weeks if the participant starts a new complement inhibitor. For participants with PNH who enroll into the silo under crovalimab treatment, additional time under crovalimab previous to enrollment will be

evaluated from available data requested at enrollment or from the Core Registry at baseline. Dates of exposure to crovalimab and doses administered will be collected and characterized.

For pregnancy and infant outcomes, exposure is defined as the period from 9 months (Based on the average estimated crovalimab terminal half-life of 53.1 days reported in the studies of crovalimab) prior to the DOC until the date of delivery. For breastfeeding outcomes, exposure is defined as the duration from 9 months previous the start of breastfeeding until the infant's first birthday or the date breastfeeding ends, whichever comes first.

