9.2.3 Participant Follow-up

The follow-up period will be the time period from index date (as defined in Section 9.2.1) until the end of the study or censoring, whichever comes first.

To evaluate AESIs and other AEs and SAEs for all participants with PNH, the date of censoring will be defined as the earliest occurrence of any of the following events:

- Consent withdrawal
- Site termination
- Crovalimab treatment discontinuation¹ (with an extra follow-up period after discontinuation)
- Enrollment into an interventional clinical trial²
- Death

To assess safety events during pregnancy and breastfeeding, including pregnancy and infant outcomes, additional censoring events will be defined:

- Date of delivery (for pregnancy safety and outcomes)
- First year of the infant's life (for safety and infant outcomes)
- On the date when breastfeeding stops or first year of the infant's life (for breastfeeding)

[figure not shown]
¹ For participants with PNH censored due to crovalimab treatment discontinuation, follow-up will continue up to 12 months if the participant does not start a new complement inhibitor or for 12 weeks if the participant starts a new complement inhibitor.

² To preserve the integrity of data collected for any interventional therapy for PNH in clinical studies, as well as to avoid duplicate safety reporting, participant data collection will be paused from the Crovalimab Silo and the Core Registry when participants enroll in an interventional clinical study for a PNH therapy.

Note: Safety events from the mother will continue to be recorded even after pregnancy ends, delivery, or the cessation of breastfeeding. Similarly, infant safety events will also continue to be recorded through their first year of age if breastfeeding is suspended.

Evaluation of pregnancy and infant outcomes during crovalimab exposure will rely on prospectively collected data within the Crovalimab Silo only for participants who enroll into the silo before being pregnant. However, for participants who enroll into the Crovalimab Silo while being pregnant, retrospective data on crovalimab exposure and outcomes will be incorporated into the silo, if such data are available from the Core Registry. Data for participants whose pregnancy outcomes occur before their enrollment in the Crovalimab Silo will not be obtainable. Very few instances are expected in these latter two scenarios due to the timing of drug approvals and site initiations in the Core Registry (see Figure 3).

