9.7.2 Subgroup and Sensitivity Analyses

Subgroup and sensitivity analyses will be implemented when sample size allows.

Analyses will be presented separately for all participants with PNH, for pregnant female participants with PNH, for all infants, and for infants sub-grouped by breastfeeding status (yes/no).

When feasible, analyses will be further detailed according to each trimester of pregnancy and each quarter within the infant's first year of development.

To account for previous complement inhibitor exposure, subgroup analyses will be also based on previous PNH treatment exposure, using the following definitions: "naïve new users" when individuals initiate crovalimab without prior exposure to C5 inhibitors, and "Prevalent new users" when individuals initiate crovalimab after having received at least one C5 inhibitor any time prior to crovalimab treatment start. Safety events will be also described by causality.

Potential confounding factors influencing safety and pregnancy outcomes, such as demographic information (e.g., age, race/ethnicity), clinical characteristics, maternal medical history, obstetrical history, comorbidities, and concomitant medications will be described among participants with PNH who experience an AESI, as well as for pregnancy or infant outcomes. If needed, subgroup analysis will be performed and AESIs proportions and incidence rates will be compared between subgroups.

Similarly, subgroup analysis may include clinical and laboratory test outcomes for PNH (e.g., MAVEs, HDA, BTH, etc.) and previous PNH treatment.

Sensitivity analysis will be performed restricting the data to safety events and crovalimab exposure that was collected prospectively only. The effects of the timing of crovalimab exposure before and during pregnancy and cumulative exposure periods on each outcome will be also evaluated as sensitivity analysis. Sensitivity analysis may also include timing variations of FTT and development deficiency outcomes, when available.

Full details on all statistical analyses, including other subgroup and sensitivity analyses, will be described in the Statistical Analysis Plan (SAP).

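### Section 9.3.1.1 counts the post-discontinuation follow-up window as crovalimab exposure, so identical dosing gives exposure durations 281 days apart depending on the next drug

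*Protocol*

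**What the plan says.** Section 9.3.1.1 defines exposure for all participants: "Crovalimab exposure will be defined as the duration from the date of silo enrollment until crovalimab discontinuation date, plus 12 months" if no new complement inhibitor is started, or "plus 12 weeks if the participant starts a new complement inhibitor". Crovalimab use before enrollment stands outside this duration: "additional time under crovalimab previous to enrollment will be" evaluated separately from available data. The section also says: "Dates of exposure to crovalimab and doses administered will be collected and characterized".

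Section 9.2.3 uses the same two periods as a follow-up rule. After discontinuation, "follow-up will continue up to 12 months if the participant does not start a new complement inhibitor or for 12 weeks" if one is started.

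Pregnancy has its own definition: "For pregnancy and infant outcomes, exposure is defined as the period from 9 months" before conception until delivery. That window is explicitly based on the "average estimated crovalimab terminal half-life of 53.1 days". No such basis is given for the 12 months or the 12 weeks.

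Section 9.7.1 counts person-time for incidence rates from the index date to the first event or censoring. Section 9.7.2 adds that the effects of exposure timing before and during pregnancy and "cumulative exposure periods on each outcome will be also evaluated as sensitivity analysis".

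**The concern.** Following participants after they stop is sensible here, because hemolysis after discontinuation is one of the safety concerns in Section 7. Calling that follow-up time exposure is a different step, with three consequences.

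- The reported duration includes time after dosing has ended, so it is overstated for participants who stop.
- The length of the added time depends on the next treatment. Durations for switchers and non-switchers are then not on the same scale, even when their crovalimab dosing was identical.
- The same time is part of AESI follow-up. A single pooled rate therefore covers both the period on drug and the period after it. An event that can arise only around a dose is spread over time in which it cannot occur. An event provoked by stopping is counted as arising during exposure.

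At stake is how the exposure tables and AESI rates are read in a study meant to describe long-term safety.

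**Working it through.** **Inputs.** Half-life 53.1 days; added periods of 12 months (365.25 days) or 12 weeks (84 days); pregnancy window of 9 months (273.9 days). All are from Section 9.3.1.1, with 30.4375 days to the month.

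**The one window with a stated basis.** Section 9.3.1.1 gives the half-life but not the multiple. Assuming five half-lives, 5 × 53.1 = 265.5 days = 8.7 months, which agrees with the stated 9 months.

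**The three windows against the same half-life.** Fraction of drug left = 0.5^(t/53.1).

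| Window | Days | Half-lives | Drug left |
|---|---|---|---|
| 12 weeks | 84 | 1.58 | 33.4% |
| 9 months | 273.9 | 5.16 | 2.8% |
| 12 months | 365.25 | 6.88 | 0.85% |

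One all-participant window ends with a third of the drug left. The other runs about 3.3 months past five half-lives (12 − 8.7).

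**Defined exposure for identical dosing.** The gap is fixed at 365.25 − 84 = 281 days (9.2 months). Defined exposure is time on drug since enrollment plus the added period, assuming that period is completed.

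| Months on drug | No new inhibitor | New inhibitor | Ratio |
|---|---|---|---|
| 3 | 15.0 | 5.8 | 2.60 |
| 6 | 18.0 | 8.8 | 2.05 |
| 12 | 24.0 | 14.8 | 1.63 |
| 24 | 36.0 | 26.8 | 1.35 |
| 60 | 72.0 | 62.8 | 1.15 |

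Measured by time on drug, every ratio is 1.00.

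**Share of cohort person-time.** The protocol gives no discontinuation or switching rates, so these are assumptions: 10% to 50% stop after 1 or 2 years on drug, and the rest have 4 years on drug. Share = added time / (time on drug + added time).

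Worked case: 30% stop after 1 year and 80% of those switch.
- Time on drug: 0.3 × 1 + 0.7 × 4 = 3.10 years per participant.
- Added time: 0.3 × (0.2 × 1 + 0.8 × 84/365.25) = 0.115 years.
- Share: 0.115 / 3.215 = 3.6%.

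Over the full range the share is 0.6% to 4.4% if everyone who stops switches, and 2.6% to 16.7% if nobody does.

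**Effect on rates.** Section 9.3.1.2.7 limits infusion- and injection-related reactions to the time of administration and the 24 hours after it. Ignoring truncation at first events, their rate is multiplied by about (1 − share), or 0.964 in the worked case. Hemolysis works the other way: footnote d of Table 1 lists serious hemolysis in participants who discontinue, and the pooled rate does not separate it from on-treatment events.

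**The case against.** The strongest defence is that the window is deliberate and its effect small. Hemolysis after stopping was raised by regulators, and immune complex reactions can occur on switching away, so events after the last dose must be captured. A shorter window after a new inhibitor plausibly limits attribution of that drug's events to crovalimab. With a 53.1-day half-life, much of the added time is not drug-free. Section 7 expects stopping without switching to be unlikely, so the 12-month case should be uncommon. Dates and doses are collected, and the study is descriptive. All of this stands. It justifies the follow-up rule and limits the size of the problem, but it does not justify using that rule as the measure of exposure.

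A reader might go further and infer that the definition distorts AESI results by cumulative exposure. The documents do not support that, for two reasons.

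- The cumulative-exposure sentence in Section 9.7.2 is a sensitivity analysis that opens with exposure around pregnancy, which has its own definition. Whether its reference to each outcome includes AESIs is unclear, and no grouping by total exposure is specified.
- The added time is not what would produce such a distortion. This was checked by simulation under a constant AESI rate of 4 per 100 person-years. Assumptions: entry over the first 5 of 6 years, other discontinuation 8% a year, 80% switching. If 25% to 50% of AESIs lead to stopping, grouping by exposure as defined gives about 21 to 35 per 100 person-years below 12 months. Grouping by time on drug alone still gives about 16 to 26, and a uniform 9-month period about 20 to 37. If no AESI leads to stopping, the protocol definition gives 4.1, 4.0 and 4.0 below 12, at 12–36 and above 36 months. The gradient is reverse causation from grouping by total duration, a method the protocol does not state.

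Nor should the definition be read as covering the whole treatment course: it begins at silo enrollment.

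**Conclusion.** The point holds as a flaw in the exposure definition. Followed as written, Section 9.3.1.1 reports exposure that depends on the next drug, with a fixed gap of 281 days for identical dosing. The relative difference is about twofold after six months of dosing and 15% after five years. The two periods have no stated basis and are not reconciled with the half-life used in the same section.

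At cohort level the effect is small. The added time is about 3% of total exposure under the simulation inputs above, with the wider range in the working if switching is rarer or stopping more common. Dilution of rates for dosing-bound AESIs is of that order. The loss of the distinction between on-treatment and post-discontinuation events matters more for interpretation, particularly for hemolysis. The effect on person-time assumes that censoring falls at the end of the extra follow-up period, which is how Section 9.2.3 reads.

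**What to change.** - **Section 9.3.1.1:** define exposure duration for all participants from the collected dose dates, and include crovalimab time before enrollment where available. If a residual-drug period is to be counted, make it the same for everyone and state its basis.
- **Section 9.2.3:** keep the 12-month and 12-week periods here only, as the follow-up or risk window.
- **Section 9.7.1:** report AESI rates separately for on-treatment and post-discontinuation time.
- **Section 9.7.2:** say whether the cumulative-exposure analysis covers AESIs. If it does, use exposure accrued up to the event or censoring date.

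The cost is wording and ordinary splitting of person-time, with no new data. Total reported exposure becomes slightly smaller, by about 3% under the assumed inputs.

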9.3.1.2 Primary Safety Variables

9.3.1.2.1 Serious Infections

The presence, type, onset and resolution date and hospitalizations for the reason of serious infections will be described.

9.3.1.2.2 Meningococcal Infections and Other Infections with Encapsulated Bacteria

The presence, type, onset and resolution date and hospitalizations for the reason of Meningococcal and other infections with encapsulated bacteria will be described.

9.3.1.2.3 Development or Worsening of any Neurological Condition

Examples of neurological conditions include axonal neuropathy and multifactorial mononeuropathy will be described, including onset and resolution date.

9.3.1.2.4 Malignancies and Hematologic Abnormalities

The presence and type of malignancy, onset and resolution date will be described.

9.3.1.2.5 Serious Hemolysis

Serious hemolysis, onset and resolution date will be described. This event includes the following:

- New or worsening symptoms of PNH: fatigue, hemoglobinuria, abdominal pain, shortness of breath (dyspnea), anemia (hemoglobin < 10 g/dL), dysphagia, backache, headache, erectile dysfunction, chest discomfort, jaundice and other symptoms with detailed specification. Onset and resolution dates, and duration of symptoms will also be collected.
- Serious hemolysis, identified by serum lactate dehydrogenase (LDH) levels greater than the pretreatment level, along with any of the following: greater than 25% absolute decrease in PNH clone size (in the absence of dilution due to transfusion) in ≤ 1 week; a hemoglobin level of ≤ 5 g/dL or a decrease of > 4 g/dL in ≤ 1 week; angina; change in mental status; a 50% increase in serum creatinine level; or thrombosis.

Additionally, to contextualize hemolysis, the MAH will abstract the following:

- Possible alternative causes for the episode of hemolysis, including the presence of any complement-activating conditions.
- Proportion of PNH cells in granulocytes, monocytes, erythrocytes Type II/III, and reticulocytes.
- All medications used to treat or prevent the events of serious hemolysis.

9.3.1.2.6 Transient Immune Complex Reactions

All TICRs should be captured as a diagnosis of “transient immune complex reactions” in the AE eCRF, including the onset and resolution date. Associated signs and symptoms should be recorded in the dedicated TICR eCRF of the Crovalimab Silo.

9.3.1.2.7 Infusion- and Injection-related Reactions

All IRRs, occurring during or within 24 hours after crovalimab administration will be described. All reactions should also be evaluated to determine if they were related to studied medicinal product infusion or injection, and therefore, captured as a diagnosis (e.g., "infusion-related reaction", "injection-site reaction", or "anaphylactic reaction"). If possible, ambiguous terms such as "systemic reaction" should be avoided. Associated signs and symptoms should also be recorded. If a patient experiences both a local and systemic reaction to the same dose of studied medicinal product, each reaction will be recorded separately, with signs and symptoms also recorded separately on the dedicated Crovalimab Silo eCRF.

9.3.1.3 Secondary Variables

9.3.1.3.1 Adverse Events and SAEs (not included as AESI)

An adverse event is defined as any untoward medical occurrence in a patient administered a medicinal product and which does not necessarily have a causal relationship with this treatment. An AE can therefore be:

- Any unfavorable and unintended sign (including an abnormal laboratory finding), symptom, or disease temporally associated with the use of a medicinal product, whether or not the event is considered causally related to the use of this medicinal product.
- Any new disease or exacerbation of an existing disease (a worsening in the character, frequency, or severity of a known condition).
- Recurrence of an intermittent medical condition (e.g., headache) not present at baseline.
- Any deterioration in a laboratory value or other clinical test (e.g., electrocardiogram [ECG], X-ray) that is associated with symptoms or leads to a change in study treatment or concomitant treatment or discontinuation from study medicine.

Serious Adverse Events

The terms “serious” and “severe” are not synonymous. The term “severe” is often used to describe the intensity (severity) of a specific event according to NCI CTCAE criteria; however, the event itself, may be of relatively minor medical significance (such as a severe headache). This is not the same as “serious”, which is based on event outcome or action criteria usually associated with events that pose a threat to a patient’s life or functioning. Seriousness (not severity) serves as a guide for defining regulatory reporting obligations.

An SAE is an AE that meets any of the following criteria:

- Results in **death** of a patient.
- Is **life-threatening**: This refers to an event/reaction in which the patient was at risk of death at the time of the event/reaction; it does not refer to an event/reaction which hypothetically might have caused death if it were more severe.
- Requires **inpatient hospitalization**: An event/reaction that results in an admission to the hospital for any length of time. This does not include an emergency room visit or admission to an outpatient facility.
- Results in **prolongation of existing hospitalization**: An event/reaction that occurs while the study patient is hospitalized and prolongs the patient's hospital stay.
- Is a **congenital anomaly/birth defect**: An anomaly detected at or after birth, or any anomaly that results in fetal loss.
- Results in **persistent or significant disability/incapacity**: An event/reaction that results in a condition that substantially interferes with the activities of daily living of a study patient. Disability is not intended to include experiences of relatively minor medical significance such as headache, nausea, vomiting, diarrhea, influenza, and accidental trauma (e.g., sprained ankle).
- Is a **medically important event or reaction**: An important medical event/reaction that may not be immediately life-threatening or result in death or hospitalization, but based on medical judgment may jeopardize the patient and may require medical or surgical intervention to prevent any of the outcomes listed above (i.e., death of patient, life-threatening, hospitalization, prolongation of hospitalization, congenital anomaly/birth defect, or persistent or significant disability/incapacity). Examples of such events include allergic bronchospasm requiring intensive treatment in an emergency room or at home, blood dyscrasias or convulsions that do not result in inpatient hospitalization, or the development of drug dependency or drug abuse.
- Any suspected transmission via a medicinal product of an infectious agent is also considered as a SAE.

All AESIs, AEs, and SAEs will be recorded, including their corresponding dates and characteristics such as outcome, treatment, hospitalization, severity, seriousness, and de-/rechallenge.

9.3.1.3.2 Clinical Outcomes and Laboratory Test Results Relevant to PNH Among Participants who Experienced an AESI

The following clinical outcomes and laboratory test results related to PNH will be recorded among participants with PNH who experience an AESI:

- Major adverse vascular events (MAVEs), including thrombosis
 - If yes, type of event
- Red blood cell transfusions
 - Yes/No
 - Number of units received
- Breakthrough hemolysis (BTH)
 - Physician-defined BTH
 - Protocol-defined BTH
 - ≥ 1 new or worsening sign or symptom of intravascular hemolysis (fatigue, hemoglobinuria, abdominal pain, dyspnea, anemia [hemoglobin < 100 g/L], MAVE [including thrombosis], dysphagia, or erectile dysfunction) and elevated LDH ($\geq 2 \times$ the upper limit of normal [ULN]) after prior LDH reduction to $< 1.5 \times$ ULN on therapy
- High disease activity (HDA) status
 - Evidence of intravascular hemolysis (LDH $\geq 1.5 \times$ ULN) and any of the following symptoms: fatigue, hemoglobinuria, abdominal pain, shortness of breath (dyspnea), anemia (hemoglobin < 100 g/L), MAVE (including thrombosis), dysphagia, or erectile dysfunction
- Development or worsening of autoimmune disease
 - If yes, type of event
- Bone marrow pathology
 - If yes, type of bone marrow pathology or other hematological disorder, % hemoglobin, absolute reticulocyte count, LDH, LDH \times ULN, LDH ratio, haptoglobin, indirect and total bilirubin, AST/ALT, direct antiglobulin test

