Analyses will be presented separately for the entire PNH participant cohort, pregnant female participants with PNH, all infants, and infants categorized by breastfeeding status (yes/no). When feasible, these analyses will be further detailed according to each trimester of pregnancy and each quarter within the infant's first year of development. Additionally, where data allows, outcomes will be analyzed based on prior PNH treatment and using the classifications of naïve new users and prevalent new users.

Potential confounding factors influencing safety and pregnancy outcomes, such as demographic information (e.g., age, race/ethnicity), clinical characteristics, maternal medical history, obstetrical history, comorbidities, and concomitant medications will be used in subgroup analyses among participants with PNH who experience an AESI, as well as for pregnancy or infant outcomes. Adverse events of special interest proportions and incidence rates will be compared between subgroups. Similarly, subgroup analysis by clinical and laboratory test outcomes for PNH will be performed when feasible. Safety events will be also described by causality.

Sensitivity analysis will be performed restricting the data to safety events and crovalimab exposure that was collected prospectively only. The effects of the timing of crovalimab exposure before and during pregnancy and cumulative exposure periods on each outcome will be also evaluated as sensitivity analysis. Sensitivity analysis may also include timing variations of failure to thrive (FTT) and development deficiency outcomes, when available.

Full details on all statistical analyses, including other subgroup and sensitivity analyses, will be described in the Statistical Analysis Plan (SAP).

MILESTONES

FIRST DATA EXTRACTION:

The date of first data extraction is the date when the variables used for the data analysis as per protocol are extracted for the first time. The planned first data extraction is after 6 months of Crovalimab Silo inception. The planned first data extraction is in Q1 2026.

LAST DATA EXTRACTION:

The last data extraction is the date of the end of the Crovalimab Silo registry, plus an additional 6 months to account for final data transfer. The planned last data extraction is in Q2 2032.

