Obstetric history ^g	X		
Pregnancy status, outcome and maternal complications	X	X	X
AEs, adverse fetal/neonatal/infant outcomes and baby complications, including growth and development deficiency ^h		X	X
Breastfeeding information	X	X	X
Vaccination	X	X	X
Fatigue questionnaire ⁱ	X	X	

Data	Baseline (Enrollment Visit) ^a	Follow-up ^b	Participant Discontinuation of Crovalimab/Registr y Completion ^c
------	---	------------------------	--

AE = adverse event; ASEI = adverse event of special interest; FACIT = Functional Assessment of Chronic Illness Therapy; LDH = lactate dehydrogenase; MAVE = major adverse vascular event; PNH = paroxysmal nocturnal hemoglobinuria; SAE = serious adverse event; ULN = upper limit of normal.

- ^a Data from baseline will include information collected in the core and at the enrollment visit.
- ^b Data are expected to be entered in the electronic data capture system approximately every 6 months post-enrollment. Every participant will be followed up during their entire crovalimab treatment and up to 12 months after discontinuation of crovalimab, if they do not start a new complement inhibitor (or 12 weeks if they start a new complement inhibitor).
- ^c After discontinuation from crovalimab, participants with PNH would be followed up for 12 months from the discontinuation date of crovalimab (if they do not start a new complement inhibitor) or up to 12 weeks after discontinuation (if they start a new complement inhibitor).
- ^d Including serious infections, Meningococcal infection, development or worsening of any neurological condition (e.g., axonal neuropathy, multifocal mononeuropathy, etc.), malignancies and hematologic abnormalities, serious hemolysis in participants with PNH who discontinue crovalimab, transient immune complex reactions, and infusion and injection related reactions. Treatment, hospitalizations, outcomes and causality for AESIs, AEs, and SAEs will be also collected.
- ^e Including, but not limited to MAVEs (including thrombosis), packed red blood cell transfusions, breakthrough hemolysis, high disease activity status (evidence of $LDH \geq 1.5 \times ULN$ with any of the following symptoms: fatigue, hemoglobinuria, abdominal pain, shortness of breath, anemia (hemoglobin < 100 g/L), dysphagia, erectile dysfunction, development or worsening of autoimmune disease, bone marrow pathology and hematological disorders, impaired renal function, impaired hepatic function, and death.

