9.7.1 Safety Analyses

No formal statistical testing will be performed. Descriptive statistics will be reported using summary tables and figures (where appropriate). Continuous variables will be summarized using mean, standard deviation, median, range (min–max) and interquartile range. Categorical variables will be summarized using counts and proportions (%).

Additionally, incidence and incidence rate (IRs; in person-years) and their 95% CIs of AESIs, SAEs and AEs will be calculated. The exact 95% CIs will be computed using the Clopper-Pearson method (Clopper and Pearson 1934). For the calculation of IRs, the denominator will be the pooled person-time of all the participants within the cohort. The patient time–at-risk will be calculated from index date until the date of an incident event or censoring, whichever occurs first. All first events occurring during follow-up period will be counted in the total number of events (thus, for each participant, only the first event will be counted) and divided by the total patient-years at risk. In addition, to IRs, incidence proportions will be calculated as proportion of participants with PNH afflicted with each of the AESIs, SAEs, and AEs up to the data extraction date.

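### Section 9.3.1.3.2 limits recording of MAVE, transfusion, BTH and HDA to participants with an AESI, against Table 1; if the dataset followed it, the optional AESI subgroup comparison would be conditioned on the outcome

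*Protocol*

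**What the plan says.** Section 9.3.1.3.2 defines the recording population for the PNH clinical outcomes: "The following clinical outcomes and laboratory test results related to PNH will be recorded among participants with PNH who experience an AESI". The list that follows includes MAVE, red blood cell transfusion, physician-defined and protocol-defined BTH, and HDA. The second secondary objective in 8.2 is confined to the same participants.

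Section 9.3.3 says that silo data are collected according to Table 1. The clinical events and outcomes row there is marked at baseline, follow-up and discontinuation/completion. Its footnote e reads "Including, but not limited to MAVEs (including thrombosis), packed red blood cell transfusions, breakthrough hemolysis, high disease activity status", and footnote b says "Every participant will be followed up during their entire crovalimab treatment and up to 12 months after discontinuation of crovalimab". Neither mentions an AESI.

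On analysis, the synopsis states "Adverse events of special interest proportions and incidence rates will be compared between subgroups" and then "Similarly, subgroup analysis by clinical and laboratory test outcomes for PNH will be performed when feasible". Section 9.7.2 is softer: "Similarly, subgroup analysis may include clinical and laboratory test outcomes for PNH (e.g., MAVEs, HDA, BTH, etc.) and previous PNH treatment". For whole-cohort frequency, 9.7.1 covers three classes of event: "incidence rate (IRs; in person-years) and their 95% CIs of AESIs, SAEs and AEs will be calculated".

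**The concern.** The protocol fixes the recording population for the same items in two incompatible ways. A baseline entry cannot depend on an AESI that happens later, so both statements cannot hold as written.

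This matters because the study analyses registry data at second hand: the variable definition decides what is extracted and therefore what can be analysed. Comparing AESI frequency between participants with and without MAVE, HDA or BTH needs the status of participants who never had an AESI. A programmer who builds the dataset from 9.3.1.3.2 would leave that status out.

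Separately, section 7 names thrombosis as the leading cause of severe complications and death in PNH. Yet no section plans a proportion or rate of the MAVE composite, protocol-defined BTH or transfusion among all crovalimab users.

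**Working it through.** The protocol has no figure of its own on this point. Its only computed table, Table 2, reproduces (for example 1 − 0.995^300 = 77.8%), but nothing here depends on it.

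**1. The texts side by side**

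- Recording population: participants with an AESI (9.3.1.3.2); all participants, from baseline (9.3.3, Table 1 and footnotes b and e).
- Needed for the subgroup comparison in 9.7.2: MAVE, HDA and BTH status in participants with and without an AESI.
- Denominator for incidence rates in 9.7.1: pooled person-time of the whole cohort. Under the 9.3.1.3.2 wording, the person-time of AESI-free participants could not be assigned to any MAVE, HDA or BTH subgroup.

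**2. What conditioning on an AESI does to the comparison**

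Let M be MAVE (or HDA, or BTH), A any AESI, and A_j one particular AESI. Since A_j implies A,

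P(A_j | M, A) = P(A_j | M) / P(A | M).

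Dividing by the same expression for participants without M gives

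observed ratio = RR_j / RR_any,

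where RR_j and RR_any are the true risk ratios, M against no M, in the whole cohort.

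- Pooled any-AESI endpoint: RR_any / RR_any = 1, whatever the truth.
- A single AESI: the true ratio divided by RR_any. It is right only if RR_any = 1.

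Illustration with assumed values, because the protocol gives no any-AESI risk, MAVE risk or risk ratio. Take any-AESI 20%, MAVE 5% and RR_any = 2.

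- P(A | no M) = 0.20 / (0.05 × 2 + 0.95) = 19.0%; P(A | M) = 38.1%.
- Suppose serious infection is unrelated to MAVE, at the 6% quoted from the crovalimab trials in 9.5. Among AESI participants it would read 6 / 38.1 = 15.7% with MAVE and 6 / 19.0 = 31.5% without, a ratio of 0.5 where the truth is 1.
- For RR_any from 1 to 3 the observed ratio for such an AESI runs from 1 down to 0.33.

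**3. What it does to the description of MAVE**

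With the same assumptions, 15 of 300 participants (5.0%) have a MAVE and 60 have an AESI. Of the 15, 15 × 0.381 = 5.7 are in the AESI group, where MAVE reads 5.7 / 60 = 9.5%. The inflation factor is RR_any / (m × RR_any + 1 − m), with m the MAVE risk. For RR_any 1 to 3 and m 2% to 10% it lies between 1 and 2.9. Some excess is plausible because thrombosis is itself one criterion of the AESI serious hemolysis (9.3.1.2.5).

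**4. How far BTH would be lost**

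Protocol-defined BTH has 8 qualifying signs. The symptom limb of serious hemolysis begins "New or worsening symptoms of PNH: fatigue, hemoglobinuria, abdominal pain, shortness of breath (dyspnea), anemia (hemoglobin < 10 g/dL), dysphagia" and also lists erectile dysfunction. It therefore contains 7 of the 8, all but MAVE (hemoglobin < 10 g/dL equals < 100 g/L). Read literally, few BTH cases would fall outside the AESI group. The gap is mainly the MAVE composite and transfusion.

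**5. If Table 1 governs**

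Status is known for everyone, no conditioning occurs, and the comparison estimates RR_j directly. What remains is that no whole-cohort row is planned for the three outcomes.

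**The case against.** The strongest reply is that collection is already settled. Section 9.3.3 makes Table 1 the silo's schedule, and 9.3.1.3.2 sits in a variables section serving an objective that is consistently limited to participants with an AESI. On that view, recorded is a loose word for described. This is the more natural reading, and it stands as far as data availability goes. It does not remove the conflict in the text, which an analyst should not have to resolve by guessing.

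A reader might infer that the subgroup comparison cannot be done at all, or that the AESI proportion would be 100% in every subgroup. The documents do not support either. Section 9.7.1 defines proportions for each AESI, and no pooled any-AESI endpoint is named. Even on the literal reading, single-AESI proportions and rates would differ between subgroups; they would be biased rather than degenerate.

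The analysis is also optional: 9.7.2 says it may be included, both places make it depend on sample size, and details are left to an SAP that is not shown. An optional analysis should still be sound under the protocol's own variable definition.

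Finally, the AESI-only objective is a legitimate choice, and single thromboses and reported BTH enter whole-cohort AE/SAE rates without an AESI condition. That stands. Whole-cohort rows for the composite, BTH and transfusion are an improvement and do not correct an error.

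**Conclusion.** The internal conflict is real and worth correcting, at a modest, secondary level. Its harm is conditional. If the dataset follows 9.3.1.3.2, the comparison by MAVE, HDA or BTH is uninformative for any AESI and off by a factor of 1 / RR_any for each single AESI, and the three outcomes are described only in a group selected on a post-index event. If it follows Table 1, the comparison is feasible.

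No primary estimate is affected under either reading. The numbers of MAVE or transfusion participants left out cannot be calculated from the protocol; the figures in the working rest on assumed risks and show direction and mechanism only. It would be wrong to read this point as saying that thrombosis goes uncounted.

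**What to change.** - **9.3.1.3.2:** state that these items are recorded and extracted for all participants as in Table 1, and are additionally described among those who experience an AESI.
- **9.7.2 and synopsis:** use all participants for the MAVE, HDA and BTH subgroups, and take HDA status at baseline, where Table 1 already schedules it, so that it precedes the events being compared.
- **9.7.1, with a matching phrase in the second secondary objective:** add descriptive whole-cohort proportions and incidence rates with 95% CIs for the MAVE composite, BTH (physician-defined and protocol-defined) and transfusion. Keep the AESI-only description.

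The cost is wording in a few sections, a slightly wider secondary objective and a few extra descriptive tables. Table 1 already schedules the items for everyone, so no new data collection is needed.
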